#### **8.3.2.4. Vital Signs**

Vital signs will be measured at each visit after the subject has been in the supine position for a minimum of 5 minutes and will include temperature, systolic and diastolic blood pressures, HR, and respiratory rate. For subjects who are unable to lie down, the vital signs can be measured after the subject has been in a seated position for 5 minutes.

Postural changes in systolic and diastolic blood pressures, HR, and respiratory rate will be measured within 3 minutes after standing. For subjects who are unable to stand, the postural change in these parameters can be made in the seated position.

Body weight will also be recorded at each visit and height will be recorded only at Screening (Visit 1). Abnormal vital signs that are clinically significant should be recorded as AEs on the eCRF.

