**Table 14: Windows of Relative Time Used to Classify Subject Assessments (Study RVT-101-2001)**

Period	Visit Number	Nominal Day	Actual Study Day 	
			Lowest	Highest
Screening (Week -6) 	1	-29		-1
Run-in (Week -2) 	2	-14	-39	-1
Baseline (Week 0)	3	1	1	1
On Treatment				
Week 1	4	7	2	10
Week 2	5	14	11	20
Week 4	6	28	21	35
Week 6	7	42	36	49
Week 8	8	56	50	63
Week 10	9	70	64	77
Week 12	10	84	78	105
Week 18	11	126	106	147
Week 24	12	168	148	last dose+7
Follow-up (Week 26)/ET	13	182	+7	

 Actual study day is derived by (visit date – run-in date) + 1 for Screening visit; (visit date – first dose date) + 1 for other visits except for Screening visit.

 Visit window for Screening visit is relative to run-in visit instead of Baseline visit.

 Visit windows may be adjusted to account for 2 10-day extensions to the run-in period allowed per protocol.

For data where two or more assessments are slotted into the same visit interval, the data recorded closest to the target visit day will be used for the summary tables and analyses. If two

assessments are equally close to the target day, the later of the two assessments will be used in tabulations and analyses; data from the earlier assessment(s) will be listed only.

- Note that for safety data analysis by visit (except blood pressure or heart rate assessments), the closest assessment is always the assessment used, however, for efficacy, if the closest assessment is not evaluable (or is missing), the other assessment would be used. For example, for ADAS-Cog, if the total score could not be calculated for the closest assessment, another assessment would be used. For “anytime” analysis of the safety data, all data points will be used.
- If on one of the dates only one blood pressure measurement is available (ie, only one of either the supine, sitting or standing measurements), then the assessments recorded on the other date, which slots to the same visit interval, will be used in tabulations and analyses. A similar rule applies for pulse rate assessments.
- Orthostatic blood pressure and heart rate will be calculated using vital sign measurements from whatever 2 body positions they are collected. If vital signs are collected in all 3 body positions (supine, sitting and standing), the supine and standing measurements will be used to calculate orthostatic blood pressure and heart rate.

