### 10.3. Vital Signs

Vital sign data (blood pressure [BP], pulse rate, and weight) will be summarized by treatment, visit, and planned time and listed by subject, visit, treatment, planned time and actual date and time. Change from baseline will also be summarized. The incidence of PCS values will be presented, with a focus on new-onset PCS values by visit and at ANY TIME. Orthostatic BP measurements will also be tabulated using the PCS criteria.

PCS ranges for these parameters are provided in [Table 18](#).

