**Table 18: List of Potentially Clinically Significant Ranges for Vital Sign Parameters (Study RVT-101-2001)**

Systolic blood pressure:
Low: < 90 and decrease ≥30 mm Hg
High: ≥ 180 and increase ≥ 20 mm Hg
Diastolic blood pressure:
Low: < 50 and decrease ≥20 mm Hg
High: >90 and increase ≥20 mm Hg
Pulse
Low: <50 bpm and Decrease ≥30 bpm
High: >100 and Increase ≥30 bpm

Weight
≥ 10% increase from baseline
≥ 10% decrease from baseline
Orthostatic Hypotension
≥ 30 mmHg decrease (reduction) in SBP upon positional change
≥ 20 mmHg decrease (reduction) in DBP upon positional change

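### Orthostatic change is pooled over non-comparable position pairs under one 30/20 mmHg criterion, so by-visit and new-onset counts mix a change of manoeuvre with a change in blood pressure

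*SAP*

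**What the plan says.** **Collection.** In Protocol 8.3.2.4 the default is a supine reading after five minutes and a second reading within three minutes of standing. A subject who cannot lie down may be seated for the first reading. For the second: "For subjects who are unable to stand, the postural change in these parameters can be made in the seated position". Three position pairs are therefore permitted: supine-to-standing, seated-to-standing and supine-to-seated.

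**Derivation.** SAP 7.7.2, in the rules after Table 14: "Orthostatic blood pressure and heart rate will be calculated using vital sign measurements from whatever 2 body positions they are collected". A preference follows, but only for complete data: "If vital signs are collected in all 3 body positions (supine, sitting and standing), the supine and standing measurements will be used". A date with a single reading is handled separately, in a rule that opens "If on one of the dates only one blood pressure measurement is available (ie, only one of either the supine, sitting or standing measurements" and sends the analysis to the other date in the same visit window.

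**Criterion.** SAP Table 18 gives two limits under orthostatic hypotension, "≥ 30 mmHg decrease (reduction) in SBP upon positional change" and "≥ 20 mmHg decrease (reduction) in DBP upon positional change". Neither names a pair.

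**Reporting.** SAP 10.3: "Orthostatic BP measurements will also be tabulated using the PCS criteria". Potentially clinically significant (PCS) vital signs are presented "with a focus on new-onset PCS values by visit and at ANY TIME". The section gives no split by pair, no not-evaluable category, no denominator for the orthostatic rows and no requirement that Baseline and later visits use the same pair.

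**The concern.** Orthostatic change in blood pressure and heart rate is a named safety endpoint in both documents. Parkinsonism is a core diagnostic feature in this population, so inability to stand is foreseeable, and the protocol provides for it.

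Two consequences follow.

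- **Within a visit.** A supine-to-seated reading is a different manoeuvre from standing up. If it falls short of 30/20 mmHg, the table cannot show whether the subject stood without a drop or never stood.
- **Across visits.** A subject who stood at Baseline but is seated for the second reading on treatment has changed manoeuvre. A drop that standing would have shown can go unseen at that visit. The reverse switch, seated at Baseline and standing later, can produce an apparent new-onset value. If losing the ability to stand is related to the effect being monitored, the choice of pair depends on the outcome.

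At stake is the interpretability of one safety table, in particular its by-visit and new-onset rows.

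**Working it through.** The plan states no orthostatic rate, share unable to stand or power for this endpoint, so there is no figure to reproduce. The check sets the rules side by side and then scales the effect on stated assumptions.

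**Step 1: what each permitted pair yields**

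| Positions recorded | Orthostatic value derived? | Criterion applied | Measures a standing drop? |
|---|---|---|---|
| Supine, standing | Yes | 30/20 mmHg | Yes |
| Seated, standing | Yes | 30/20 mmHg | Yes, from a different starting position |
| Supine, seated | Yes | 30/20 mmHg | No |
| All three | Yes, from supine and standing | 30/20 mmHg | Yes |
| One position only | No pair on that date; the other date in the window is used; nothing is stated if there is none | None | No |

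The SAP ranks supine and standing first when all three positions exist. With only two, it treats all pairs alike.

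**Step 2: scale of the dilution (all inputs assumed)**

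Let f be the share of subjects unable to stand, and s the sensitivity of supine-to-seated at the same cut-off relative to standing. Assume the same underlying rate in subjects who can and cannot stand. Then

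observed incidence = true incidence × [1 − f(1 − s)]

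| f | s = 0 | s = 0.5 |
|---|---|---|
| 5% | 1 − 0.05 × 1 = 95% | 1 − 0.05 × 0.5 = 97.5% |
| 10% | 1 − 0.10 × 1 = 90% | 1 − 0.10 × 0.5 = 95% |
| 20% | 1 − 0.20 × 1 = 80% | 1 − 0.20 × 0.5 = 90% |

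With assumed true rates of 10% and 20% in two arms, the 10.0-point difference reads as 8.0 points at f = 20%, s = 0 (8% against 16%). It reads as 9.0 points at f = 20%, s = 0.5 (9% against 18%).

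**Step 3: in subjects**

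With 80 per arm and f = 10%, 80 × 0.10 = 8 subjects per arm would be on a supine-to-seated pair. That is not 8 missed events. At a true rate of 20%, missed events are 8 × 0.20 × (1 − 0.5) = 0.8 per arm at s = 0.5, and 8 × 0.20 × 1 = 1.6 at s = 0.

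**Step 4: unequal shares between arms (assumed)**

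Take a true rate of 20% in both arms, with f = 5% in one and 20% in the other. At s = 0 the observed rates are 0.20 × 0.95 = 19.0% and 0.20 × 0.80 = 16.0%, a spurious 3.0 points in favour of the arm where more subjects cannot stand. At s = 0.5 they are 19.5% and 18.0%, a gap of 1.5 points. Nothing in the documents says the shares will differ.

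**The case against.** A reader might infer three stronger things. The documents support none of them.

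- **That subjects who cannot stand are counted as normal.** Table 18 applies to any positional change, so a supine-to-seated fall that reaches either limit is flagged. If sitting elicited 40-60% of the standing systolic fall (an assumption), a 40 mmHg standing fall would read 16-24 mmHg and be missed. Standing falls from 50 mmHg (30/0.6) to 75 mmHg (30/0.4) upwards would still be caught. The diastolic limb is a second route to a flag.
- **That a subject seen only seated contributes a zero change.** The SAP derives the value from two positions and treats a date with one as inadequate. On a plain reading no value results. The SAP is silent only on what follows when there is no other date.
- **That a later change of pair erases an earlier drop.** The fall is computed within a visit, and any-time safety analyses use all data points. A standing drop already recorded on treatment stays in the any-time table.

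The rest of the opposing case has weight. Standing is the protocol default. The safety analysis is descriptive, with no test or decision rule on this endpoint. Dizziness, fainting and falls are asked about at every visit whatever the position, falls are analysed separately, and clinically significant vital signs are recorded as adverse events. Confining the main table to subjects who can stand would also condition on a post-randomisation state and drop the subjects of most interest.

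These arguments limit the size of the problem and shape the remedy. They do not make the pairs comparable or tell the reader which manoeuvre lies behind a count.

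**Conclusion.** The point holds as one of comparability. The SAP expressly pools different manoeuvres under one criterion and does not require the same pair when Baseline is compared with later visits. The result is lower or unknown sensitivity for supine-to-seated pairs, no separation of those subjects from subjects who stood without a drop, and by-visit and new-onset counts that a change of pair can move in either direction.

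The overall dilution is modest: observed incidence is 80% to 97.5% of true incidence, given 5-20% unable to stand, relative sensitivity of 0 to 0.5 and equal underlying rates. If subjects who cannot stand have a higher underlying rate, the loss is larger. Changes of pair that differ by arm would matter more, but the documents give no basis for saying they will occur. The primary and secondary efficacy conclusions are unaffected. This is an inexpensive improvement to a safety table that is worth making before unblinding.

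**What to change.** In SAP 7.7.2 and 10.3:

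- Keep the all-pairs orthostatic PCS table on the Safety Population, so that no subject or flagged event is lost.
- Add orthostatic PCS incidence by position pair, with supine-to-standing, seated-to-standing and supine-to-seated shown separately, each with its own stated denominator.
- Count new-onset orthostatic values only where Baseline and the post-baseline visit use the same pair. Events after a change of pair remain visible in the all-pairs and pair-specific tables.
- Show single-position assessments as not evaluable when no other date in the window supplies a pair.
- Report, by arm and visit, how many subjects lack a standing reading and how many have changed pair since Baseline.

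The cost is SAP wording, a few more table rows and small denominators in some pair-specific rows. No new data should be needed, because the present derivation rule already presumes that body position is recorded. No clinical threshold changes.

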### **7.7.3. Imputation Rules for Missing Start and Stop Dates of Prior and Concomitant Medications, Adverse Events and Birth Dates**

For analyses of AEs and concomitant medication usage, a complete date must be established in order to correctly identify the AE or medication as occurring during treatment or not. For purposes of imputing missing components of partially-reported start and stop dates for AEs and for medication use, the algorithms listed below will be followed. Start and stop dates of AEs or concomitant medication will be displayed as reported in the subject data listings (ie, no imputed values will be displayed in data listings).

Missing start day, but month and year present:

- If the date of the first dose of double-blinded study medication is in the same month and year as the occurrence of the AE/concomitant medication, the start day of the event/concomitant medication will be assigned to the day of the first dose of the double-blinded medication.
- Otherwise the start day will be set to the 1st day of the month.

Missing start day and month, but year present:

- If the first dose of double-blinded study medication in the same year as the occurrence of the AE/concomitant medication, the start day and month will be assigned to the date of the first dose of the double-blinded medication.
- Otherwise the start day and month will be set to January 1st.

Missing end day, but month and year present:

- The end day will be set to the last day of the month.

Missing end day and month, but year present:

- The end day and month will be set to the maximum of the date of study termination or the date equivalent to 30 days after the last dose of the double-blinded medication.
- However, if the study termination year and year for the date of the last dose of the double-blinded medication +30 days are greater than the event/concomitant medication year, the day and month are to be set to December 31st.

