#### **8.3.2.1.3. Time Period and Frequency for Collecting Adverse Event and Serious Adverse Event Information**

Collection of AEs and SAEs will begin at the time a subject signs informed consent and continue until the follow-up visit. SAEs that are spontaneously reported by the subject or subject representative or discovered by the investigator or designee after the follow-up visit and up to 30 days after the last dose of IP must be collected and reported.

All SAEs will be recorded and reported to PPD or Axovant Sciences within 24 hours of the investigator becoming aware of the SAE.

Investigators are not obligated to actively seek AEs or SAEs in former study subjects. However, if the investigator learns of any SAE, including a death, at any time after a subject has been discharged from the study, and he/she considers the event reasonably related to the investigational product or study participation, the investigator must promptly notify the sponsor or sponsor representative.

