#### **7.4. Analysis Populations**

It is intended that a complete accounting of patients for the analysis populations will be provided, from the Screening Population through the Per-Protocol Population.

- Screening Population: All patients who are screened (signed an informed consent) will be included in the Screening Population.
- Placebo Run-In Population: All patients who took at least 1 dose of IP in the Placebo Run-in will be included in the Placebo Run-In Population. This population will be used to provide an accounting of the disposition of patients during this phase of the study.

- Randomized Population: The Randomized Population will include all patients who are randomized.
- Safety Population: All subjects who were randomized and took at least one dose of double-blind investigational product.
- Intent-to-Treat (ITT) Population: All subjects randomized to treatment who have taken at least one dose of double-blind investigational product and who have a baseline and at least one post baseline primary efficacy assessment for the UPDRS-III **or** for the ADAS-Cog 11. This will be the primary population used for the efficacy analysis of all variables EXCEPT the UPDRS Part III and Part 5.
- UPDRS Primary Analysis Population: This will be the primary population used for the UPDRS Part III efficacy analysis, and is comprised of all ITT patients EXCLUDING those with no change OR a worsening in UPDRS-III total score prior to a dose increase in anti-parkinsonian medication (including but not limited to L-dopa, dopamine agonists, and monoamine oxidase inhibitors) and where there is *subsequent* improvement or stabilization of UPDRS-III total score.
  - Dose increase in anti-parkinsonian medication is defined as an increase in dose, dose frequency or commencement of anti-parkinsonian medication where the total daily dose of anti-parkinsonian medication at Week 24 is higher than at Baseline.
- UPDRS Sensitivity Analysis Population: All ITT patients EXCLUDING those who increase or start anti-parkinsonian medication treatment during the double-blind treatment period.
  - Dose increase in anti-parkinsonian medication is defined as an increase in dose or frequency or commencement of anti-parkinsonian medication where the total daily dose of anti-parkinsonian medication at Week 24 is higher than at Baseline.

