### 7.7.1. Handling of Incomplete Dates

Where necessary for the calculation of derived variables, partial dates will be completed using the earliest calendar date based on the partial date provided. This rule is valid for all partial dates with the exception of the following:

- Start and stop dates of adverse events
- Start and stop dates of concomitant medication
- Start and stop dates of double-blinded medication

Imputation rules for start and stop dates for the above 3 categories are described in Section 7.7.3.

Completely missing dates will not be replaced and the corresponding derived variables will be set to missing.

Note that for missing DLB diagnosis date, if the month is missing, January will be imputed. If the day is missing, the 1st of the month will be imputed. Thus, if a patient has only a year of diagnosis, then the imputed diagnosis date will be January 1 of that year.

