### 10.1. Adverse Events (AEs)

Adverse events will be tabulated by MedDRA system organ class (SOC) and preferred term, unless otherwise specified.

- Adverse events occurring prior to the first dose of single-blind study medication (ie, prior to the Placebo Run-In period) will be presented as Screening events.
- Adverse events occurring on or after the first dose of single-blind study medication but prior to the first dose of double-blind study medication will be presented as Placebo Run-In events.
- Adverse events occurring on or after the first dose of double-blind study medication, and within 7 days of the last dose of double-blind study medication, will be referred to as On-Treatment AEs (OTAEs).
- Events occurring after that will be presented as Post-Treatment. While the Post-Treatment period is defined as up to 30 days post-last-dose, it is possible some events may be reported that start after that 30 day period. These events will be included in the analysis.

Tabulations of the incidence of AEs will be presented as follows:

- Screening (using the Screening Population as the denominator).
- Single-Blind Placebo Run-In (using the Placebo Run-In Population as the denominator)
  - AEs
  - AEs resulting in discontinuation from study

- SAEs. SAEs will be tabulated (separately) as All SAEs, Non-Fatal SAEs and Fatal SAEs.
- Double-Blind Treatment Period (using the Safety Population as the denominator)
  - OTAEs. OTAEs will also be presented by the defined subgroups.
  - OTAEs occurring in  $\geq 5\%$  and  $10\%$  in EITHER Intepirdine treatment arm. These thresholds may be adjusted as the data dictate.
  - OTAEs judged by the investigator to be at least possibly related to study medication
  - OTAEs by maximum intensity (Grade 1 mild, Grade 2 moderate, and Grade 3 severe)
  - OTAEs resulting in discontinuation from study medication
  - SAEs. SAEs will be tabulated (separately) as All SAEs, Non-Fatal SAEs and Fatal SAEs.
  - SAEs judged by the investigator to be at least possibly related to study medication
  - An analysis of Adverse Reactions (defined as events occurring with higher incidence in either Intepirdine arm than in the Placebo arm) will be provided via a tabulation of these OTAEs.
- Post-Treatment Period (using the Safety Population as the denominator)
  - AEs
  - SAEs (Fatal and Non-Fatal)

A listing off deaths will be presented.

The time to first onset of OTAEs will be presented using the following bins of onset:

- 0 to 2 weeks

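### SAP 7.7.3 moves a partial AE or medication start to the first double-blind dose date without checking a known stop date or a pre-dose record, so an event that ended before dosing can be counted as on-treatment

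*SAP*

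**What the plan says.** SAP 7.7.3 gives its own purpose: "a complete date must be established in order to correctly identify the AE or medication as occurring during treatment or not". It has two start-date branches.

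- Day missing, month and year present: if the first double-blind dose falls in that month and year, "the start day of the event/concomitant medication will be assigned to the day of the first dose of the double-blinded medication". If not, the 1st of the month is used.
- Day and month missing, year present: if the first double-blind dose falls in that year, "the start day and month will be assigned to the date of the first dose of the double-blinded medication". For any other year, "Otherwise the start day and month will be set to January 1st".

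No further condition is attached. SAP 7.7.1 sends AE and medication dates to this section and adds only that "Completely missing dates will not be replaced and the corresponding derived variables will be set to missing".

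Two sets of results depend on the completed date. SAP 10.1 defines on-treatment AEs (OTAEs) as "Adverse events occurring on or after the first dose of double-blind study medication, and within 7 days of the last dose" of double-blind medication. In SAP 7.4, the UPDRS Sensitivity Analysis Population leaves out ITT patients who increase or start anti-parkinsonian medication during the double-blind period. A dose increase there covers a rise in dose or frequency, or commencement, with a higher total daily dose at Week 24 than at Baseline. The UPDRS Primary Analysis Population uses nearly the same definition ("an increase in dose, dose frequency or commencement of anti-parkinsonian medication", with the same dose condition). The UPDRS Per-Protocol Population is built from the Sensitivity Population.

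**The concern.** Assigning the first-dose date is a sensible default when timing is unknown. Here it also applies when timing is partly known. Protocol 8.3.2.1.3 states "Collection of AEs and SAEs will begin at the time a subject signs informed consent", so the database will hold events that began and ended in screening or placebo run-in. If such an event has a partial start in the dosing month or year, the rule overrides its recorded stop date.

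The misplaced event then enters the OTAE tables. It also enters the 0 to 2 week onset bin and the tabulation of adverse reactions in SAP 10.1. That tabulation lists any event with a higher incidence in either intepirdine arm than in placebo, with no minimum difference, so one misplaced event can add or remove a row.

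For medications, the issue is membership of the UPDRS populations. Levodopa is not on the list of conditional medications that must be stable for 30 days before Screening (Protocol 6.2, criterion 3, and Table 1), so a start shortly before the study is compatible with entry. If the record gives the year only, the rule places that start inside the double-blind period.

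**Working it through.** The plan attaches no figure to this rule, and its power calculation does not depend on it. The check is to apply the rule as written and then ask how often a truly pre-dose partial start would be moved.

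**Worked cases** (illustrative first dose 20 June 2017):

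| Record | Start under SAP 7.7.3 | Result |
|---|---|---|
| AE, start ?? June 2017, stop 10 June 2017 | 20 June 2017 | OTAE; start after stop |
| AE, start ?? May 2017, stop 28 May 2017 | 1 May 2017 | pre-dose; correct |
| Drug, start 2017, stop 15 March 2017 | 20 June 2017 | start after stop |
| Drug, start 2017, ongoing | 20 June 2017 | Day 1 start |
| Drug, start April 2017 | 1 April 2017 | pre-dose; correct |
| Drug, start 2016, ongoing | 1 January 2016 | pre-dose; correct |

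The first and third rows are wrong on the record's own evidence. The fourth is wrong if the drug was already recorded as in use at Screening.

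**How often a partial start would be moved.** Assumptions, not in the documents: first-dose dates uniform over a 365-day year, and true onset uniform over the W days before dosing.

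- Day missing: an onset k days before dosing shares the dosing month if the day of the month of first dose exceeds k. Over a year this gives the sum of L(L−1)/2 over months of length L: 7×465 + 4×435 + 378 = 5,373 date-and-lag pairs. For W of 30 or more, the share moved is 5,373/(365W).
- Day and month missing, W below 365: the share moved is 1 − (W+1)/730. For W = 730 it is (365×364/2)/(365×730) = 66,430/266,450.

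Windows: 42 days for AEs is 28 of screening plus 14 of run-in. The longest pre-dose AE window under Protocol 8.1 is 28 + 14 + 14 + 5 + 20 = 81 days. For drugs, 224 days is about six months (182 days, the look-back in Protocol 7.9.1) plus 42. Two years (730 days) is shown for contrast.

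| Pre-dose window | Day missing | Day and month missing |
|---|---|---|
| AE, 42 days | 35% | 94% |
| AE, 81 days | 18% | 89% |
| Drug, 224 days | 7% | 69% |
| Drug, 730 days | 2% | 25% |

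These shares are conditional on the start being partial and truly pre-dose. Only the part with a known pre-dose stop or a pre-dose record is misplaced against available evidence. For that part, the rule as written moves every record whose partial start shares the dosing month (day missing) or dosing year (day and month missing). The guarded rule moves none.

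**Does a Day 1 drug start remove a patient from a UPDRS population?**

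- SAP 7.7.2 starts the double-blind period on the date of first dose, so a Day 1 start lies inside it.
- SAP Table 14 puts Baseline on Day 1, and SAP 8.6 defines new-onset medication as starting only after the first-dose date. On those definitions, a drug starting on Day 1 can be read as Baseline use, and an unchanged dose is then no increase.
- SAP 7.4 does not say which reading governs the Baseline dose. Exclusion from the Sensitivity Population, and so from UPDRS Per-Protocol, is left open.
- Exclusion from the Primary Analysis Population also needs UPDRS-III unchanged or worse before the increase, and improved or stabilised afterwards. UPDRS-III is first scheduled at Visit 3 (Protocol Table 2; SAP Table 2), so there is no scheduled earlier interval in which the first condition could be shown for a Day 1 start.

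**The case against.** The best defence is that the rule is conservative. It favours counting events as on-treatment, it applies alike in all arms, and the safety analysis is descriptive (SAP 10). AEs are reviewed at every visit, and source notes must carry start and end dates (Protocol Table 2 and 11.1.5), so partial dates for recent AEs should be uncommon. Listings show dates as reported.

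Much of this stands where timing is unknown. It does not defend overriding a known stop date, because a start after the recorded stop is wrong under any imputation policy. Nor do the listings expose the problem: they omit imputed dates, so the contradiction sits only in the data behind the tables. Protocol 10.4.5.1 asks for a note on whether a Day 1 AE came before or after dosing, so the order evidently matters to the sponsor.

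A reader might infer more than the documents support. One tempting reading is that long-standing anti-parkinsonian drugs become on-study starts. They do not: a year-only start in an earlier year goes to 1 January of that year. Another is that a moved drug has a Baseline dose of zero, which the SAP nowhere says. A third is that the primary UPDRS analysis loses patients through this rule, which the conditions in SAP 7.4 and the visit schedule do not show. An ongoing drug also counts as concomitant in the double-blind period wherever its start falls (SAP 8.6).

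**Conclusion.** The rule is wrong as written for AEs and medications whose records already place them before dosing. For AEs the consequence is direct: an event that ended in screening or run-in can be tabulated as on-treatment. For anti-parkinsonian drugs it is conditional: a drug started earlier in the dosing year and recorded by year only may lead to wrongful exclusion from the UPDRS Sensitivity and UPDRS Per-Protocol populations, depending on how Baseline dose is read. No effect on the UPDRS Primary Analysis Population is established.

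The overall size is unknown, because the documents do not say how many dates will be partial. The percentages in the working rest on uniform dates and chosen windows. They describe how a partial date would be treated, not how many subjects are affected. The point is worth settling before unblinding because it touches safety counts and population membership and is cheap to correct.

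**What to change.** In SAP 7.7.3, assign the first-dose date to a partial start only if both conditions hold:

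1. the reported or imputed stop date is missing, ongoing, or on or after the first double-blind dose; and
2. the item was not already recorded before first dose at Visits 1 to 3.

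Otherwise use the existing 1st-of-month or 1 January branch, and never impute a start later than a known stop.

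In SAP 7.4, state that an anti-parkinsonian drug recorded as in use at Visits 1 to 3 before first dose counts in the Baseline dose, whatever its imputed start date.

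The cost is a few lines of text and a small programming change. The conservative default stays wherever timing is truly unknown.
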